5. ENDPOINTS

5.1 PRIMARY ENDPOINTS

Relative bioavailability of volasertib and its main metabolite CD10899 will be investigated primarily on the basis of the following pharmacokinetic parameters:

CTP: *The following primary endpoints will be determined for volasertib and its main metabolite CD 10899:*

- AUC_{0-tz} *(area under the plasma concentration-time curve of the analyte in plasma over the time interval from zero to 504 hours or last actual measure time)*
- C_{max} *(maximum measured plasma concentration of the analyte in plasma)*

The primary objective is to estimate the relative bioavailability of a single dose of volasertib and its main metabolite CD10899 when administered alone (volasertib monotherapy) compared with co-administered with itraconazole (200mg once daily) in cancer patients with various solid tumors. The relative bioavailability is primarily to be determined on the basis of geometric mean ratios of the primary pharmacokinetic endpoints AUC_{0-tz} and C_{max} measured under the combination therapy period relative to mono therapy period. The derivation of these primary pharmacokinetic endpoints is given in the internal SOP 001-MCS-36-472_RD-01([6](#)).

5.2 SECONDARY ENDPOINTS

[figure not shown]
5.2.1 Key secondary endpoint

As no key secondary endpoints have been specified in the protocol, this section is not applicable.

5.2.2 Other Secondary endpoints

PK endpoints

The $AUC_{0-\infty}$ of volasertib and its main metabolite CD 10899 will be statistically assessed using the same methods as described for the primary endpoint.

[figure not shown]
5.4.1 Safety and tolerability endpoints

The assessment of safety and tolerability will be based on

- Adverse events
 - Drug related AE
 - AE leading to dosage reduction
 - AE leading to permanent treatment discontinuation
 - Serious AE

- Safety laboratory tests
- Physical examination (height, weight, ECOG)
- Vital signs (blood pressure and pulse rate)

For details please refer to the CTP Section 5.2 and 5.3.

5.4.4 *Electrocardiogram*

The following endpoints will be regarded for the electrocardiogram (ECG) analysis:

- Absolute QTcF intervals at each time point
- QTcF changes from individual baseline at each point in time: (QTcF post-baseline measurement obtained at each time point) – (individual baseline QTcF measurement)

The above endpoints will also be computed for the uncorrected QT interval, for heart rate (HR), PR interval and QRS complex. HR will be derived from RR intervals as described in [section 7.8.3](#).

. The classifications will be performed separately for cycle 1 and cycle 2 as well as using the maximum on-treatment value over the entire mono-therapy period (≥ 2 cycles) per patient.

- QTcF values at individual baseline and maximum post-baseline:
 - ≤ 450 ms
 - >450 ms to ≤ 470 ms
 - >470 ms to ≤ 500 ms
 - >500 ms
- QT values at individual baseline and maximum post-baseline:
 - ≤ 500 ms
 - >500 ms
- QTcF increase from individual baseline to the maximum post-baseline value:
Intervals for a given patient as
 - ≤ 30 ms
 - >30 ms to ≤ 60 ms
 - >60 ms
- QT increase from individual baseline to the maximum post baseline value:
Intervals for a given patient as
 - ≤ 60 ms
 - >60 ms
- Increase from individual baseline $\geq 25\%$ and absolute value >200 ms of all on-treatment values in PR interval for a given patient
- Increase from individual baseline $\geq 25\%$ and absolute value >110 ms of all on-treatment values in QRS interval for a given patient

All endpoints derived for the QTcF interval will also be derived for the QTcB interval. The derivation of each QTc interval from the RR and QT intervals is described in [section 7.8.3](#).

[figure not shown]
The QTc threshold of 470 ms is used to be consistent with the Common Terminology Criteria for Adverse Events (CTCAE), version 3.0, which is widely accepted as a standard for describing and managing safety findings in clinical studies of anticancer therapy. The other QT/QTc thresholds are in accordance with the ICH E14 Guideline.

Notable findings (defining outliers for the QT/QTc interval) at any on-treatment time point for a given patient are defined as

- Maximum increase from individual baseline to on-treatment value in QTc interval > 60 ms
- QT/QTc > 500 ms in any on-treatment value which is not present at individual baseline

All endpoints involving the ‘individual baseline’ will also be derived for the ‘combined baseline’ (refer to [Section 6.7](#)).

ECG endpoints will also include cardiologist’s assessments. In particular, findings of abnormal rhythm, conduction, morphology, ST segment changes, T wave abnormalities and myocardial infarction will be explored.

6. GENERAL ANALYSIS DEFINITIONS

6.1 TREATMENTS

In total, it was planned to include 24 patients in this two period trial with a fixed treatment sequence:

Treatment A: Day -3 to Day 15 of cycle 1: daily 200mg itraconazole

Day 1 of cycle 1: Single dose volasertib infusion 300mg

Treatment B: Day 1 of cycle 2 (Day 23 starting from Day 1 of cycle 1): Single dose volasertib infusion 300mg

For detail of dosage and formulation see section 4.1 in CTP. For detailed information on the handling of the treatment in the O*C views refer to Technical TSAP ADS plan

Time intervals for safety analysis are defined below. The analyses for safety endpoints will focus the on-treatment period of volasertib and contrast the safety profile within first cycle and second cycle during the study period. In addition, the safety endpoints will be summarized for the entire volasertib mono-therapy period.

Screening period: Screening to first dose of Itraconazole.

Itraconazole induction period: Start of first dose of Itraconazole to start of first dose of volasertib.

First cycle combo-therapy period: Start of first dose of volasertib to the start of the second cycle if patients received the second cycle mono-therapy, or to the 21 days after the first volasertib administration date if patients discontinued after the first cycle.

Second cycle mono-therapy period: Start of second dose of volasertib to the start of the cycle 3 if patients received cycle 3 mono therapy, or to the 21 days after second volasertib administration date if patients discontinued after the second cycle.

Mono-therapy period: Start of the second dose of volasertib to the last dose of volasertib plus 21 days.

Post-treatment period: After 21 days after last dose of volasertib.

6.2 IMPORTANT PROTOCOL VIOLATIONS

[Table 6.2: 1](#) contains the categories in which important PVs are classified. Categories for manually assessed important PVs, i.e. important PVs that are detected manually at the sites and cannot be detected through the database, are not shown in this table but will be finalised before DBL and documented in the final BRPM minutes.

Consistency checks will be prepared for identifying violations of time windows.

Table 6.2: 1 Important protocol violations

Category/ Code		Description	Example/Comment
A		Entrance criteria not met	
	A1	Inclusion criteria not met	Inclusion criteria 6 not met as specified in the protocol as this is safety related; see SOP) Other inclusion criteria violation will be manually reviewed.
	A2	Exclusion criteria not met	Laboratory criteria 6-11, 19. Violations on other exclusion criteria will be manually reviewed.
B		Informed consent	
	B1	Informed consent not available/not done	Informed consent date missing
	B2	Informed consent too late	Informed consent date <actual consent date> was after Visit 1 date <Visit 2 date>
C		Trial medication and randomization	

Table 6.2: 1 (continued) Important protocol violations

Category/ Code	Description	Example/Comment
C1.1	Non-compliance	Missing itraconazole doses during either pre-volasertib administration period or on the day of volasertib administration is considered IPV..
C1.2	Non-compliance	Missing itraconazole doses in the post-volasertib administration period will be documented and reviewed case by case
C2.1	Volasertib infusion late	Volasertib infusion not immediately after medicine preparation will be documented and reviewed case by case
D	Concomitant medication	
D2	Prohibited medication use	
 • Strong inhibitors of CYP3A4 • Inducers of CYP3A4 • Inhibitors of P-gp • Inducers of P-gp (CTP 4.2.2.1)
E	Missing data (for primary endpoints)¹	
E4	Certain violations of procedures used to measure primary and secondary data	Un-evaluable PK results for reasons other than study discontinuation.
F	Incorrect timing (for primary and secondary endpoints)²	
F5	Certain violations of the time schedule used to measure primary and secondary data	

KEY: Hb = haemoglobin, Hct = Haematocrit, Tx = transfusion, PPS – Per Protocol Set

6.3 PATIENT SETS ANALYSED

- **Treated set (TS):**
This patient set includes all patients who were documented to have taken at least one dose of volasertib. This is the full analysis set population in the sense of ICH-E9. It is used for safety analysis.
- **Primary pharmacokinetic set (pPKS):**
This subject set includes all patients in the TS who were treated on the same dosage

(250mg and 300mg) in the first two cycles and provided complete PK measures without important protocol violations.

- Sensitivity pharmacokinetics set (sPKS)

This subject set includes all patients in the TS who provided complete PK measures in the first two cycles without important protocol violations.

- ECG analysis set (ECGS): This patient set includes all patients in the treated set who provide at least one matching pair of QT measurements available pre-dose and after drug administration. Patients with an artificial pacemaker will be excluded.

Table 6.3: 1 Patient sets analyzed

Class of endpoint	Patient set			
	TS	pPKS	sPKS	ECGS
Primary (PK) endpoints		X	X	
Safety endpoints		X		
ECG endpoints				X
Demographic data/Medical history and Concomitant diagnosis, Concomitant therapy		X		
Important PVs	X			
Disposition		X		

[REDACTED]

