15. Chemo-, radio- immuno-, or molecular-targeted cancer-therapy within the past four weeks prior to start of therapy or concomitantly with this trial. This restriction does not apply to steroids, bisphosphonates hormonal / antihormonal treatment (e.g. in prostate or breast cancer).
16. Patients unable to comply with the protocol
17. Alcohol abuse more than an average 3 units of alcoholic beverages per day or more than 21 units per week (1 unit equals 0.5 pint [285 mL] of beer or lager, 1 glass [125 mL] of wine, 25 mL shot of 40% spirit)) or drug abuse
18. Life expectancy less than 12 weeks
19. Potent CYP 3A4 and P-glycoprotein inhibitors other than the study drug or inducers between one week prior to first drug administration or expected treatment with a respective drug until the last PK sample is collected
 - a) Strong CYP 3A4 inhibitors: atazanavir, clarithromycin, indinavir, itraconazole (other than study drug), ketoconazole, nefazodone, nelfinavir, ritonavir, saquinavir, telithromycin
 - b) CYP 3A4 inducers: carbamazepine, rifampicin
 - c) P-gp inhibitors: cyclosporine, erythromycin, itraconazole (other than study drug), ketoconazole, quinidine, phenobarbital salt with quinidine, ritonavir, valspar, verapamil
 - d) P-gp inducers: hypericum perforatum, rifampicin
20. History of allergy/hypersensitivity (including allergy to study drug or its excipients) based on the investigator's assessment
21. Excessive physical activities (within one week prior to administration and until the last PK sample is taken)

Exclusion criteria specific for this study:

22. Veins unsuitable for blood sampling and infusion

For study restrictions refer section [4.2.2](#).

Proprietary confidential information.

© 2017 Boehringer Ingelheim International GmbH or one or more of its affiliated companies. All rights reserved.
This document may not - in full or in part - be passed on, reproduced, published or otherwise used without prior written permission.

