6. INVESTIGATIONAL PLAN

6.1 VISIT SCHEDULE

The patients will stay at the investigator site from the evening before first itraconazole administration (day -4) until day 4 of the first cycle as well as from the day before intravenous infusion of volasertib until 72 hours after start of infusion of the second cycle (day -1 until day 4). Ambulatory visits will happen 168 hours (day 8), 336 hours (day 15) and 504 hours (day 22) after start of infusion, where the last visit may coincide with day 1 of consecutive treatment cycles. In this case the blood sample for PK has to be taken before administration of the study drug.

Procedures will be performed as outlined in the [flow chart](#). In third and subsequent treatment cycles the patient will visit the investigator at regular intervals as specified in the flow chart (visit 2 and 3 are optional visits at the investigator's discretion) for determination of safety laboratory parameters, recording of adverse events and additional procedures as outlined in the flow chart. If a patient misses a visit and the patient reports to the investigator between this and the next scheduled visit, the missed visit should be performed with the actual date and the reason should be given for the delayed visit. The next visit, however, should take place as scheduled relative to the first administration of the trial drug in the treatment cycle.

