6.2.3.2 Follow-up visit

Follow-up visits will be performed after the EOT visit for patients who are not eligible for further treatment cycles until progression of disease, death, treatment with any other anti-tumour therapy, patient is lost to follow-up, or agreement between sponsor and principal investigator not to pursue further follow up visits.

Follow-up visits should be performed at 3 months intervals or earlier if appropriate. Follow-up visits may also be performed by telephone interview in case the patient is unable to visit the investigator.

The following will be obtained and / or performed.

- Occurrence of AEs since last visit in case they are considered drug-related
- Follow-up of AEs in case they were not yet recovered at EOT
- ECOG performance score
- Treatment with any other anti-tumour drug
- Patient status: date of and reason for death (if applicable), date of progression (in case, the patient experienced PD)

If visit is performed by telephone interview at least information on progression, date of progression and date of death should be obtained.

After approval of Protocol Revision 3, Follow-up is completed 21 days after discontinuation of study drug.

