7.3.3 Safety analyses

All patients who receive at least one dose of study drug will be included in the safety evaluation. Safety analyses will be performed in accordance with BI standards.

Adverse events will be coded using the Medical Dictionary for Drug Regulatory Activities (MedDRA). Adverse events occurring prior to drug administration will be assigned to the screening period. Adverse events occurring within 21 days of most recent volasertib infusion will be considered to be on treatment.

Independent of this rule, the relationship of an adverse event to the study drug treatments will be assessed by the investigator. Adverse event information as reported in the eCRFs will be aggregated in a two step process. First, multiple recordings (AE occurrences) of the same adverse event will be combined into one AE episode (collapsing). The second step will combine all of the AE episodes of an adverse event into one AE record as needed for by-patient summaries (condensing).

Reporting of adverse events and laboratory data will follow the standard BI procedures. The analysis of adverse events will comprise various frequency tabulations. Tables will be produced for treatment cycle 1 (co-administration of volasertib and itraconazole), treatment cycle 2 (volasertib alone) and for all treatment cycles combined. DRTs and the MTD (see [Section 5.2.6](#)) will be reported.

Laboratory values will be listed, tabulated and compared with their reference ranges. They will also be assessed with regard to possible changes compared to baseline values and with regard to the comparison of the first and second treatment cycle. The frequency of possible clinically significant abnormalities will be tabulated.

Safety will also be assessed by evaluation of physical examination (see [Section 7.3.8](#)), vital signs (blood pressure, pulse rate) and 12-lead ECG. Change from screening and/or baseline as well as change between treatment cycle 1 and 2 will be compared descriptively.

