7.8 SAFETY ANALYSIS

All patients who receive at least one dose of volasertib will be included in the safety analyses. This is the treated set defined in [Section 6.3](#).

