7.8.1 Adverse Events

The analysis of adverse events will focus on events that occurred during the on-treatment period, defined from the first treatment administration until 21 days after the last administration for all patients who receive at least one administration of the study treatment regimen. Tables will display the results within each cohort defined by the starting dosage of volasertib.

The analysis of adverse events will be performed within each of the following three time periods separately ([Section 6.1](#)):

- First cycle volasertib+ itraconazole combo-therapy period
- Second cycle volasertib mono-therapy period
- Continued volasertib mono-therapy period.

The AEs occurred during screening period, itraconazole induction period, and post-study period ([Section 6.1](#)) will be listed.

Standard tabulations arranged by MedDRA SOC and preferred term (PT) will include:

- the overall incidence of adverse events (AE)
- AE intensity graded according to the common terminology criteria for adverse events (CTCAE) version 3

- AE judged to have been related to trial medication
- AE leading to dosage reduction
- AE leading to permanent treatment discontinuation
- AE identified associated with the protocol-specified significant event
- Serious AE

Listings will be produced for the following AEs

- Infections

Listings will be prepared of patients who are identified as having experienced any of the following AEs. Identification will be based upon modified MedDRA SMQ and HLT groupings.

- Mucositis
- QT prolongation
- Cardiac, combining the following SMQ
 - Cardiac failure
 - Ischaemic heart disease
 - Cardiac arrhythmia terms
- Hemorrhages SMQ
- Hepatic
 - AE identified by the SMQ
 - Listing of all ALT, AST, Tbili, and ALK over time, for patients with
 - 1) any ALT or AST ≥ 3 x ULN combined with elevation of total bilirubin ≥ 2 x ULN at the same time or
 - 2) an isolated elevation of AST and/or ALT ≥ 5 x ULN (without an elevation of bilirubin)

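### Taken literally, the SAP's percentage rule keeps patients who never entered cycle 2 in the cycle-2 safety denominators (minor)

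*SAP*

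**What the plan says.** SAP 6.1 states that the safety analyses will set the first cycle against the second. It starts the second-cycle period at the second volasertib dose.

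The population is the treated set. SAP 6.3: "This patient set includes all patients who were documented to have taken at least one dose of volasertib". SAP 7.8 repeats the requirement, "All patients who receive at least one dose of volasertib will be included in the safety analyses", and identifies this population as the treated set of section 6.3. No separate set is defined for patients who entered cycle 2.

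SAP section 7 gives the general rule for categorical tables: counts and percentages are shown for each treatment, and the percentages use all subjects in the relevant set. SAP 7.8.1 then splits adverse events into three periods (cycle-1 combination, cycle-2 monotherapy, continued monotherapy) and presents them by starting-dose cohort.

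On patient numbers, SAP 7.4 reports that three patients started at 300 mg, that two of them stopped after cycle 1, and that all later patients started at 250 mg. SAP section 4 mentions a single patient with 300 mg in both cycles. Protocol 3.3.6 says that patients who do not complete both cycles are replaced.

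**The concern.** A patient who had one infusion and stopped belongs to the treated set and cannot have a cycle-2 event. If that patient is counted in the cycle-2 denominator, the cycle-2 percentage falls below the rate among patients at risk. The cycle-1 percentage is not affected, because everyone in the treated set received the cycle-1 infusion. The error therefore runs one way: volasertib alone looks better, and the combination looks worse by comparison. Replacement does not cure this, because the replaced patient remains in the treated set.

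Safety is a secondary objective (Protocol 2.2), and the comparison of cycles is the stated focus of the safety analysis. There is no formal test, so the printed percentages are what a reader will compare.

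**Working it through.** The documents give no figure for these denominators, so there is none to reproduce. The patient counts can be checked: 3 patients started at 300 mg (SAP 7.4) and 2 stopped after cycle 1 (SAP 7.4), leaving 3 − 2 = 1 in cycle 2. This agrees with the single patient in SAP section 4.

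**Formula.** Printed cycle-2 percentage = true percentage among patients dosed in cycle 2 × (number dosed in cycle 2 ÷ number in the treated set).

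**300 mg cohort** (all inputs from the SAP)
- Factor: 1/3 = 0.333.
- One cycle-2 event prints as 1/3 = 33.3%; among patients at risk it is 1/1.
- With equal true rates in both cycles, the printed cycle-1 to cycle-2 ratio is 3/1 = 3.0. This rests on one patient.

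**250 mg cohort.** No non-entrant is documented, so the documented factor is 1 and no dilution is shown.

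**All patients pooled.** This applies wherever a total across cohorts is shown. The planned number is 24 (Protocol 3.3 and 7.6; SAP 6.1). The documents do not give the final size of the treated set, so both readings are shown for the two documented non-entrants.

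| Reading | Factor | True 25.0% prints as | Ratio if true rates are equal |
|---|---|---|---|
| 24 with both cycles plus 2 with cycle 1 only | 24/26 = 0.923 | 6/26 = 23.1% | 26/24 = 1.08 |
| 24 treated in all, 2 with cycle 1 only | 22/24 = 0.917 | 25.0% × 0.917 = 22.9% | 24/22 = 1.09 |

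The result hardly depends on the reading.

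**Range under assumption.** If 4 or 8 patients never entered cycle 2, on top of 24 who did, the factors are 24/28 = 0.857 and 24/32 = 0.750. A true 25.0% would then print as 6/28 = 21.4% or 6/32 = 18.8%. No passage supports 4 or 8.

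**Would a per-period N alone give a like-for-like contrast?** No. Cycle 1 would describe all treated patients and cycle 2 only those who continued. Protocol 3.3.5 makes further treatment depend on benefit, blood counts, tolerability and recovery from drug-related events. Protocol 4.1.3.1 allows a lower dose after toxicity, and SAP 7.4 confirms that some patients went from 250 mg to 200 mg in cycle 2. Correct denominators remove the dilution but not the selection.

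**The case against.** The best defence is that no programmer would do this. The section 7 rule is general, and the sentence on counts and percentages refers to each treatment. The second-cycle period cannot exist for a patient without a second infusion, and adverse events are analysed within periods. The company's reporting standards and the technical data-set plan, which are not public, may already fix the N. That makes a per-period N a plausible intention. It does not displace the one explicit denominator rule in the SAP, which says otherwise. The defence is right on size: the documented dilution is confined to a three-patient cohort and is about 8% in relative terms when pooled.

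Two stronger readings are tempting, and the documents do not support them.

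*That the safety population itself is contradictory and distorts the cycle contrast.* Protocol 7.3.3 says "All patients who receive at least one dose of study drug will be included in the safety evaluation", and SAP 7.8.1 says "for all patients who receive at least one administration of the study treatment regimen". The protocol's term is loose. Exclusion criterion 19 applies it to the perpetrator, "itraconazole (other than study drug", while sections 6.1 and 6.2.3.2 use it where volasertib is the natural meaning: "In this case the blood sample for PK has to be taken before administration of the study drug" and "Follow-up is completed 21 days after discontinuation of study drug". A reader might infer an undeclared change of population. But SAP 7.8 settles the matter by pointing to the treated set, and Protocol 7.3.3 itself defines on-treatment events by the volasertib infusion. The wording applies equally to both cycles, and no itraconazole-only patient is reported. Events in the lead-in are to be listed: "The AEs occurred during screening period, itraconazole induction period, and post-study period". This is editorial.

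*That the ECG baselines invalidate the QTc contrast.* The cycle-1 pre-infusion ECG follows three itraconazole doses (Days −3, −2 and −1). The cycle-2 one comes 504 − 336 = 168 hours, or 7 days, after the last dose if cycle 2 starts on schedule. A reader might infer bias. But Protocol 5.2.4 defines baseline as the value before the current infusion, which is valid for the acute volasertib effect. Absolute QTcF is also reported, and the planned combined-baseline analysis cancels any lead-in shift in the contrast for patients with both cycles. The documents give no itraconazole effect on QT.

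**Conclusion.** The denominator point holds as a defect in a stated rule. By the letter of SAP section 7, cycle-2 percentages include patients who could not have a cycle-2 event. The size is a factor of one third in the 300 mg cohort, which concerns one patient in cycle 2, and about 0.92 when cohorts are pooled, so 25.0% reads about 23%. The pooled figure assumes that the two documented non-entrants are the only ones and that the treated set has 24 or 26 patients. Anything larger is an assumption. If the tables were programmed with per-period Ns, the defect is one of wording only.

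Safety is descriptive and the primary pharmacokinetic analysis does not use these denominators, so the severity is minor.

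**What to change.** 1. In SAP sections 7 and 7.8, state that safety tables by period use the number of patients who received volasertib in that period as denominator, overall and within each starting-dose cohort. Print that N in each column.
2. Add a cycle-1 versus cycle-2 safety summary restricted to patients dosed in both cycles, noting how many had a reduced dose in cycle 2. This addresses selection; it does not remove the dose difference.
3. Editorial: use one wording for the safety population in Protocol 7.3.3 and SAP 6.3, 7.8 and 7.8.1.
4. Optional, and not the correction of an error: a descriptive QTcF change from the screening triplicate for cycles 1 and 2. Protocol 7.3.3 already allows change from screening.

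All of this uses data already collected. The cost is a few sentences, a few more tables and column Ns that differ between periods. Cycle-2 percentages will then describe only patients who continued, and the tables should say so.
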